## 11.8.2 Secondary Efficacy Analyses

### 11.8.2.1 NRS Symptom Scores

A descriptive summary of NRS symptom scores and absolute change from baseline results will be presented by treatment overall and within each study period. Timepoints to be included in this table are: Before IMP was taken (Pre-dose), 30 minutes after IMP taken (t=0.5 hrs), 1 hour after IMP taken (t=1 hr), 1.5 hours after IMP taken (t=1.5 hrs), 2 hours after IMP taken (t=2 hrs), 4 hours after IMP taken (t=4 hrs), 8 hours after IMP taken (t=8 hrs) and 24 hours after IMP taken (t=24 hrs). Symptoms to be presented: Nausea, Photophobia and Phonophobia.

#### Difference between treatments:

The difference in absolute NRS symptom scores and change from baseline between both treatments will be summarised by timepoint. Timepoints to be included in this table are: Before IMP was taken (Pre-dose), 30 minutes after IMP taken (t=0.5 hrs), 1 hour after IMP taken (t=1 hr), 1.5 hours after IMP taken (t=1.5 hrs), 2 hours after IMP taken (t=2 hrs), 4 hours after IMP taken (t=4 hrs), 8 hours after IMP taken (t=8 hrs) and 24 hours after IMP taken (t=24 hrs). 95% Confidence interval for the difference between treatments will also be provided.

Difference between treatments will be calculated as mentioned in section 10.15.1.

The summary will be based on Per-Protocol population.

In DDP: Table 14.2.2.1

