11.5.2 Migraine symptoms

Each subject will specify his/her most troublesome symptom at baseline (Day 1).

On the day of a migraine headache, baseline information about the headache should be recorded to verify that the headache was an acute migraine headache including headache intensity, aura, presence or absence of associated symptoms, unilaterality or bilaterality of the headache, aggravation by exercise, throbbing or nonthrobbing.

The subject's symptoms will be recorded on an 11-point Likert scale. This scale allows the subject to record the presence of the symptom from 0 = no symptoms to 10 being severe symptoms. Symptom assessments will be recorded in the subject's diary prior to dosing (t = 0 min) and at 0.5, 1, 1.5, 2, 4, 8 and 24 hours post dose. Symptoms to be recorded include nausea, photophobia and phonophobia plus the subject's most troublesome symptom (eg cognitive impairment, dizziness and functional disability) if other than nausea, photophobia or phonophobia. Episodes of vomiting will also be recorded.

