## **4.2 Sample Size Justification**

*It is planned to have 20 subjects complete the study, defined as taking one dose of IMP in each treatment period and attending the follow-up (End of study) visit.*

*Assuming up to 20% of subjects do not treat one migraine headache in each treatment period or dropout of the study, 26 subjects will be enrolled in the study.*

[figure not shown]
*If the dropout rate or non-completion rate is higher than anticipated, additional subjects may be enrolled to ensure 20 subjects complete the study.*

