### 8.1 Changes to Planned Analyses

The protocol states that, as this study is a Phase IIa proof of concept study, no formal statistical hypotheses are planned to be tested although some may be investigated as part of the data presentation. It was expected that treatment effects would be assessed using descriptive statistics only and hypothesis tests used minimally.

However, by allowing subjects to be included in the Per Protocol population with a minimum of one dose of IMP, there is a possibility that subjects will be included with efficacy results for only one treatment period and unable to have an estimate of the difference between treatments. Hence, fewer subjects will be included in the summary results and any analyses for the difference between treatments.

In order to include the results for all subjects regardless of whether they took IMP in only one or both treatment periods a mixed effects model with repeated measurements (MMRM) analysis can be undertaken. This approach will be taken for the change from baseline NRS pain score to each postbaseline timepoint for each treatment only.

The remaining endpoints of a continuous nature (change from baseline NRS symptom score, change from baseline NRS symptom score for the most troublesome symptom, subject satisfaction with IMP, subject satisfaction with IMP compared with usual medication for an acute migraine attack) may be analysed using the MMRM approach depending on the number of subjects who complete both treatment periods. The decision will be made at the blind review meeting prior to database lock.

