#### 11.8.1.3 Mixed Effect Regression Model for repeated measurements (MMRM)

A mixed effects regression model using a covariance pattern will be fitted to the absolute change from baseline in NRS pain scores at each post-IMP timepoint within each treatment period for the PP population.

The model will have fixed effects for treatment period, timepoint, treatment and the interaction between timepoint and treatment. Baseline pain score within each period will be included as a covariate. A random effect for subject will be included to capture the repeated measures nature of the design.

Least squares means and corresponding 95% confidence intervals (CI) will be presented for the mean changes from baseline for LAT8881, Placebo and the difference between LAT8881 vs. placebo at each timepoint. P-values for testing the null hypothesis that the difference in least squares means between LAT8881 and placebo at each timepoint is 0 will be declared statistically significant if the p-value <0.05.

The covariance pattern will take into account the covariance between observations in different treatment periods and the covariance between observations within the same period (i.e. between timepoints).

```
proc mixed data=; class <subject> <study period>  
<treatment> <timepoint>; model <change> = <baseline> <study  
period> <timepoint>|<treatment>; random <subject>  
<subject>*<period>; lsmeans <treatment>|<timepoint> / pdiff;  
run;
```

In DDP: Tables 14.2.1.5

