#### Difference between treatments:

The difference in absolute most troublesome symptom scores and change from baseline between both treatments will be summarised by timepoint. Timepoints to be included in this table are: Before IMP was taken (Pre-dose), 30 minutes after IMP taken (t=0.5 hrs), 1 hour after IMP taken (t=1 hr), 1.5 hours after IMP taken (t=1.5 hrs), 2 hours after IMP taken (t=2 hrs), 4 hours after IMP taken (t=4 hrs), 8 hours after IMP taken (t=8 hrs) and 24 hours after IMP taken (t=24 hrs). 95% Confidence interval for the difference between treatments will also be provided.

Difference between treatments will be calculated as mentioned in section 10.15.1.

In DDP: Table 14.2.3.1

11 point Likert Migraine Symptom Scores will be listed by subject.

In DDP: Listing 16.2.6.4

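### SAP 11.8.2 leaves the symptom comparisons unadjusted for the pre-dose score; committing to that adjustment would tighten their confidence intervals at almost no cost

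*SAP*

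**What the plan says.** **Symptom comparisons.** SAP 11.8.2.1 states for nausea, photophobia and phonophobia: "The difference in absolute NRS symptom scores and change from baseline between both treatments will be summarised by timepoint". SAP 11.8.2.3 states for the most troublesome symptom: "The difference in absolute most troublesome symptom scores and change from baseline between both treatments will be summarised by timepoint". Both add a 95% confidence interval at every timepoint, pre-dose included. SAP 10.15.1 defines the difference as the LAT8881 score minus the placebo score within subject, with no adjustment.

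**Baseline.** SAP 10.12.2 takes the pre-dose score in each period and sets no minimum. SAP 10.13 defines change as the later score minus that baseline. Symptoms are scored 0 to 10 (SAP 7.2).

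**Which attacks are treated.** SAP 4.1 and Protocol 9.3 tie dosing to a headache with pain NRS of at least 4. Neither requires any associated symptom. Protocol 11.5.2 has the most troublesome symptom named at Day 1, before either treated attack.

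**Modelling.** SAP 8 says that change over time in both primary and secondary outcomes will be examined with a model set out in Section 11.8. SAP 8.1 commits to the mixed model for pain only; symptom and most-troublesome-symptom change "may be analysed using the MMRM approach depending on the number of subjects who complete both treatment periods", to be settled at blind review. SAP 11.8.1.3 specifies the pain model: "Baseline pain score within each period will be included as a covariate". SAP 11.8.2 contains no model.

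**The concern.** The dosing rule keeps the pre-dose pain score at 4 or more, but pre-dose symptom scores can lie anywhere from 0 to 10. A subject's two attacks are separate events and may start at very different symptom levels. Raw change subtracts the whole of that starting difference, so part of the spread in the paired differences reflects which attack happened to come with nausea or light sensitivity.

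The endpoints whose baselines are least constrained are therefore the ones with no assured baseline adjustment. The rule for deciding on a model does not address this. The number of completers bears on subjects with only one treated attack, not on baseline variation. If every subject completes, the stated reason for the model disappears and the unadjusted comparison stands.

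At stake is the precision of secondary efficacy endpoints 1 and 2 in a study of about 20 pairs. There is also an internal inconsistency: a symptom model is promised, then made optional, and never specified.

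**Working it through.** **The plan's own figure.** SAP 4.2: "It is planned to have 20 subjects complete the study"; "Assuming up to 20% of subjects do not treat one migraine headache in each treatment period" or drop out; "26 subjects will be enrolled in the study". 20/(1 − 0.20) = 25, and 26 × 0.80 = 20.8, so 26 is consistent with 20 pairs. No effect size, SD, correlation or symptom prevalence is given for any endpoint. Everything below rests on assumed values.

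**One discordant pair.** Suppose the pre-dose score is 0 on LAT8881 and 6 on placebo, and both are 0 at 2 hours. The changes are 0 and −6, so the change difference is 0 − (−6) = +6, against the drug, although both attacks ended alike. The absolute-score difference is 0. If a symptom is present in a share p of attacks, independently, the expected number of discordant pairs among 20 is 40p(1 − p): 10 at p = 0.5, 8.4 at 0.7 and 3.6 at 0.9.

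**Variance.** Let D0 and D1 be the within-subject treatment differences before and after dosing, with common variance s² and correlation r.
- Raw change: Var(D1 − D0) = 2s²(1 − r)
- Absolute score: Var(D1) = s²
- D1 adjusted for D0: s²(1 − r²)
- Adjusted relative to raw change: (1 − r²)/[2(1 − r)] = (1 + r)/2
- Adjusted relative to absolute score: 1 − r²

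| Assumed r | (1+r)/2 | CI narrower than raw change | 1 − r² | CI narrower than absolute score |
|---|---|---|---|---|
| 0.3 | 0.65 | 1 − √0.65 = 19% | 0.91 | 1 − √0.91 = 5% |
| 0.6 | 0.80 | 1 − √0.80 = 11% | 0.64 | 1 − √0.64 = 20% |

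These are large-sample ratios. With 20 pairs and a normal covariate, estimating the slope multiplies the adjusted variance by about 1 + 1/(20 − 3) = 1.06 on average. The gain over raw change then becomes 1 − √(0.65 × 1.06) = 17% at r = 0.3 and 1 − √(0.80 × 1.06) = 8% at r = 0.6.

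**Simulation.** 6,000 trials of 20 pairs per scenario, with integer scores from 0 to 10. Assumed: residual SD 2 (half that where the symptom is absent), post-on-pre slope 0.6, a nominal 2-point effect where the symptom is present and none where it is absent. Ranges cover between-attack correlations of 0.3 and 0.6.

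| Symptom present pre-dose | Mean, raw change | Mean, adjusted | SE, raw change | SE, absolute score | SE, adjusted |
|---|---|---|---|---|---|
| 50% | −0.86 | −0.85 | 0.63–0.68 | 0.57–0.59 | 0.47–0.48 |
| 70% | −1.21 | −1.21 | 0.67–0.70 | 0.60–0.64 | 0.52–0.53 |
| 90% | −1.54 | −1.56 | 0.64–0.67 | 0.62–0.64 | 0.57 |
| about 100% | −1.72 to −1.74 | −1.72 to −1.74 | 0.60–0.62 | 0.60–0.63 | 0.58 |

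Adjustment leaves the estimate where it was and lowers its standard error, most of all where absence is common. With no drug effect (70% present, correlation 0.3), raw change and the adjusted comparison each reject 5.0% of the time at the two-sided 0.05 level.

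**The case against.** A reader might infer that keeping attacks with a pre-dose score of 0 biases the result and understates the drug's benefit. The documents do not support that. Endpoints 1 and 2 are change in symptoms with no requirement that the symptom be present, and the mean over all treated attacks is a valid estimate of that quantity. Dilution appears only if benefit is assumed to be nil when the symptom is absent at dosing, as in the simulation above. IMP is taken within an hour of pain onset, so a symptom may still emerge, and preventing it would be a benefit that those attacks reveal. Adjustment would not alter the estimate in any case.

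Other objections stand in part:
- **Much is already reported.** Absolute-score differences appear beside change and do not subtract the baseline. The pre-dose difference is tabulated, individual scores are listed, and within-subject differences are plotted. The absolute-score comparison is still unadjusted, and its shortfall grows with r.
- **Adjustment is not ruled out.** SAP 8.1 names these endpoints as candidates for the mixed model. The weakness is that this is not a commitment and that its trigger is unrelated to baseline variation.
- **The pain contrast is narrow.** The pain difference table in SAP 11.8.1.1 is just as unadjusted; only the model in 11.8.1.3 carries the covariate.
- **More p-values.** Copying the pain model to three symptoms and the most troublesome symptom over seven timepoints would give 4 × 7 = 28 p-values, with no multiplicity adjustment planned (SAP 8.4). This is why the fix asks for intervals only.
- **Method of calculation.** The gain was worked out for a regression of paired differences. The mixed model should behave similarly but will not match it exactly.

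**Conclusion.** The point holds as one of precision and specification. The committed symptom and most-troublesome-symptom comparisons are unadjusted, the pre-dose scores they depend on can differ widely between a subject's two attacks, and SAP 8, 8.1 and 11.8.2 do not agree on whether a model will be fitted. Against raw change, adjustment would narrow the confidence interval by about 11% to 19% for an assumed r of 0.6 to 0.3, or about 8% to 17% after the cost of estimating the slope in 20 pairs. Against the absolute-score difference the large-sample gain runs the other way in r: 20% at 0.6 and 5% at 0.3. These figures assume equal variances before and after dosing and an r that the documents do not supply.

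False-positive error is not inflated, and the estimate is not biased for the stated endpoint. The outputs are exploratory, so the cost of leaving the plan as it is would be wider intervals and an analysis choice left open until blind review.

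**What to change.** 1. In SAP 11.8.2.1 and 11.8.2.3, commit, whatever the number of completers, to a model for each symptom and for the most troublesome symptom with the structure of 11.8.1.3 and the period-specific pre-dose score of that symptom as covariate. Report estimates and 95% confidence intervals by timepoint, labelled exploratory, without p-values.
2. Amend SAP 8 and 8.1 to agree with this, removing the completer-count trigger for these endpoints. In SAP 10.12.2, name the pre-dose score as baseline for the most troublesome symptom too; the section lists only pain, nausea, photophobia and phonophobia.
3. Optionally, report by treatment how many attacks had a pre-dose score of 0, and add a supportive summary limited to attacks scoring 1 or more. Keep it supportive. It answers a different question, and pairs run out quickly: with the symptom present in half of attacks, only 20 × 0.5² = 5 subjects would have it in both if attacks were independent (6 to 7 with the simulated correlations).

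The cost is SAP wording and a few tables. No new data are needed, and the descriptive tables can stay as planned.

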### 11.8.2.2 Time-Trend Plots

Time-trend plots may be created for symptom scores over time by subject and symptom. Each subject and symptom will be presented in a separate plot. X-axis will be the timepoint (hours) and Y-axis will be the NRS pain score. Plots will be grouped by treatment. There may be one or two trend lines per subject based on the number of periods the subject took IMP.

Time trend plots will be created to visualise and compare changes over timepoints in the symptom score for subjects in the Per-Protocol population. Mean values of change from baseline within each treatment group along with standard error bars will be plotted on y-axis, and timepoints will be plotted on the x-axis. Treatment groups will be displayed side-by-side in a single page.

Difference in symptom scores between both treatments for each subject will also be plotted using time trend plots. Difference between LAT8881 60 mg and Placebo will be plotted in y-axis and timepoints will be plotted in x-axis.

Difference between treatments will be calculated as mentioned in section 10.15.1.

In DDP: Figure 14.2.2.2, Figure 14.2.2.3 and Figure 14.2.2.4

### 11.8.2.3 Most Troublesome Symptom

Descriptive summary of most troublesome symptom scores and absolute change from baseline results will also be presented by treatment overall and within each study period. Timepoints to be included

in this table are: Before IMP was taken (Pre-dose), 30 minutes after IMP taken (t=0.5 hrs), 1 hour after IMP taken (t=1 hr), 1.5 hours after IMP taken (t=1.5 hrs), 2 hours after IMP taken (t=2 hrs), 4 hours after IMP taken (t=4 hrs), 8 hours after IMP taken (t=8 hrs) and 24 hours after IMP taken (t=24 hrs). Both categorical and continuous summaries will be provided in a single table.

The summary will be based on Per-Protocol population.

#### Difference between treatments:

The difference in absolute most troublesome symptom scores and change from baseline between both treatments will be summarised by timepoint. Timepoints to be included in this table are: Before IMP was taken (Pre-dose), 30 minutes after IMP taken (t=0.5 hrs), 1 hour after IMP taken (t=1 hr), 1.5 hours after IMP taken (t=1.5 hrs), 2 hours after IMP taken (t=2 hrs), 4 hours after IMP taken (t=4 hrs), 8 hours after IMP taken (t=8 hrs) and 24 hours after IMP taken (t=24 hrs). 95% Confidence interval for the difference between treatments will also be provided.

Difference between treatments will be calculated as mentioned in section 10.15.1.

In DDP: Table 14.2.3.1

11 point Likert Migraine Symptom Scores will be listed by subject.

In DDP: Listing 16.2.6.4

#### **11.8.2.4 Time-Trend Plots**

Time-trend plots may be created for most troublesome symptom scores over time by subject and symptom. Each subject will be presented in a separate plot. X-axis will be the timepoint (hours) and Y-axis will be the NRS pain score. Plots will be grouped by treatment. There may be one or two trend lines per subject based on the number of periods the subject took IMP.

Time trend plots will be created to visualise and compare changes over timepoints in the most troublesome symptom score for subjects in the Per-Protocol population. Mean values of change from baseline within each treatment group along with standard error bars will be plotted on y-axis, and timepoints will be plotted on the x-axis. Treatment groups will be displayed side-by-side in a single page.

Difference in most troublesome symptom scores between both treatments for each subject will also be plotted using time trend plots. Difference between LAT8881 60 mg and Placebo will be plotted in y-axis and timepoints will be plotted in x-axis.

Difference between treatments will be calculated as mentioned in section 10.15.1.

In DDP: Figure 14.2.3.2, Figure 14.2.3.3 and Figure 14.2.3.4

#### **11.8.2.5 No Headache Pain**

Number and percentage of subjects who achieve 'no headache pain' (NRS pain score 0 or 1) at each timepoint will be presented by treatment overall. Presence or absence of pain will be determined as

mentioned in section 10.15.4. The paired difference in number of subjects with no headache pain (LAT8881 – Placebo) will be calculated as mentioned in section 10.16.

In DDP: Table 14.2.4

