#### 3.2 Secondary Objectives

- 1. To evaluate the effect of oral LAT8881 on migraine-associated symptoms compared with placebo, when assessed by the change in symptoms based on a 11- point Likert scale*
- 2. To investigate the percentage of subjects achieving “no headache pain” following treatment with oral LAT8881 compared with placebo at any timepoint to 8 hours post dose, with no use of rescue medication*
- 3. To evaluate the safety and tolerability of single doses of oral LAT8881 in subjects with migraine headache*

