### 7.2 Secondary Efficacy Endpoints

- 1. Change in migraine-associated symptoms of nausea, photophobia and phonophobia. Symptoms are assessed on an 11- point Likert scale with 0 = no symptoms and 10 being severe symptoms at time of dosing and at 0.5, 1.0, 1.5, 2, 4, 8 and 24 hours post dose.*
- 2. Change in each subject's most troublesome symptom that may include nausea, photophobia and phonophobia cognitive impairment, dizziness and functional disability. Symptoms are assessed on an 11- point Likert scale with 0 = no symptoms and 10 being severe symptoms at time of dosing and at 0.5, 1.0, 1.5, 2, 4, 8 and 24 hours post dose.*
- 3. The percentage of subjects achieving "no headache pain" at 0.5, 1.0, 1.5, 2, 4 and 8 hours post dose.*

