### 10.15.4 Responder

Subjects achieving no migraine headache pain at each time point in each study period will be separately flagged for analysis. Presence or absence of pain will be determined as follows:

- Absence: NRS Pain score 0 or 1 at the corresponding timepoint.
- Presence: NRS Pain score more than 1 at the corresponding timepoint.

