#### 11.8.3.2 Time to First Pain-free Timepoint

The number and percentage of subjects with their first pain free timepoint will be presented by timepoint. The paired difference in the number of subjects with their first pain free timepoint will be calculated as mentioned in section 10.16.

Time taken to first pain-free timepoint will also be analysed using Kaplan-Meier curve. Time to first pain-free timepoint will be calculated based on the actual time taken from IMP as mentioned in section 10.15.5.

In DDP: Table 14.2.6.1, Figure 14.2.6.2

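### Secondary objective 2 asks for pain freedom at any time to 8 h without rescue, but its endpoint, flag and analysis give separate timepoint percentages with no rescue condition

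*SAP*

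**What the plan says.** Secondary objective 2 appears in the same terms in the protocol synopsis, protocol 4.2 and SAP 3.2. It concerns the percentage of subjects who become pain-free on LAT8881, "compared with placebo at any timepoint to 8 hours post dose, with no use of rescue medication".

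Secondary endpoint 3 (protocol 10.2, SAP 7.2) is the percentage pain-free "at 0.5, 1.0, 1.5, 2, 4 and 8 hours post dose". Rescue is not mentioned.

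The responder flag in SAP 10.15.4 is set one timepoint at a time: "Absence: NRS Pain score 0 or 1 at the corresponding timepoint". It also has no rescue condition.

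SAP 11.8.2.5 reports the number and percentage pain-free, which "at each timepoint will be presented by treatment overall". It adds: "The paired difference in number of subjects with no headache pain (LAT8881 – Placebo) will be calculated as mentioned in section 10.16". SAP 10.16 defines that difference as (b − c)/(a + b + c + d) and names no interval or test.

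Among the exploratory analyses, SAP 11.8.3.2 says: "The number and percentage of subjects with their first pain free timepoint will be presented by timepoint". Its derivation in SAP 10.15.5 takes the first record with a score of 0 or 1 and censors at 24 h.

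Rescue medication is permitted from 2 h after dosing (protocol 8.2.3, SAP 4.1).

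**The concern.** Read as written, the objective defines one yes/no outcome per treated attack: pain-free at some point up to 8 h, without rescue. That gives one paired comparison. The plan sets out a series of timepoint percentages, names none of them as the answer, and leaves out the condition that makes the outcome attributable to study treatment.

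Two things are at stake.

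- A team following SAP 11.8.2.5 exactly would not report the quantity its objective names. The reader would face several candidate answers, and the most favourable could be quoted.
- A subject who takes rescue after 2 h and is pain-free at 4 h or 8 h counts as a success for whichever treatment was taken. If rescue is commoner after placebo, this raises the placebo percentage and narrows the difference. If it is commoner after LAT8881, it does the opposite.

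**Working it through.** The plan gives no response rate, effect size or power for this endpoint, so there is no stated figure to reproduce. The only planning number used below is the 20 completers in SAP 4.2.

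**1. The definitions side by side**

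| Place | Time span | Form | Rescue condition |
|---|---|---|---|
| Objective 2 (SAP 3.2) | to 8 h | any timepoint, one outcome per treated attack | yes |
| Endpoint 3 (SAP 7.2) | 0.5 to 8 h | six separate percentages | none |
| Responder flag (SAP 10.15.4) | each timepoint | NRS 0 or 1 | none |
| Analysis (SAP 11.8.2.5) | each timepoint, no 8 h limit (SAP 10.3 also lists 24 h) | n, % and paired difference | none |
| First pain-free time (SAP 10.15.5, 11.8.3.2) | to 24 h | one first time per subject-period | in the endpoint (SAP 7.4), absent from the derivation |
| Sustained pain-free (SAP 10.15.2) | 24 h | one flag per subject-period | yes |

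The last row shows that the SAP does write a rescue condition into a derivation elsewhere.

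**2. Do the timepoint percentages determine the any-timepoint percentage?**

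Leaving rescue aside, with p_t the percentage pain-free at time t:

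max(p_t) ≤ p_any ≤ min(100%, Σ p_t)

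Assume 20 subjects, with 2, 5 and 8 pain-free at 2, 4 and 8 h and none earlier.

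- If earlier responders stay pain-free (nested groups): p_any = 8/20 = 40%.
- If different subjects respond at each time (disjoint groups): p_any = (2 + 5 + 8)/20 = 15/20 = 75%.

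Both cases print the same timepoint percentages. The direction can also reverse. LAT8881 at 2/5/8, nested, gives 8/20 = 40%. Placebo at 1/4/7, disjoint, gives (1 + 4 + 7)/20 = 12/20 = 60%. LAT8881 leads at all three times and trails on the objective's quantity. The case is extreme, but the table alone cannot rule it out.

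**3. Illustration with assumed rates**

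The ranges in the last column come from a latent-normal model with adjacent-time correlation from 0.9 down to 0.3 (200,000 draws).

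| Assumed % at 0.5, 1, 1.5, 2, 4, 8 h | Bounds | Any-timepoint % in the model |
|---|---|---|
| 2, 5, 8, 10, 20, 35 (sum 80) | 35% to 80% | 37% to 55% |
| 2, 8, 14, 20, 35, 50 (sum 129) | 50% to 100% | 53% to 74% |

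These rates and correlations are not in the documents. The table shows only that the gap above the highest single timepoint is variable.

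**4. Can the quantity be recovered elsewhere?**

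Each subject has at most one first pain-free time per period, so:

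p_any to 8 h = (sum of first-pain-free counts at 0.5, 1, 1.5, 2, 4 and 8 h) / n

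The paired version follows by collapsing at 8 h the two-way table of first pain-free times planned in protocol 14.5. Neither step is planned, and neither result carries a rescue rule.

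**5. Effect of the missing rescue condition**

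With 20 subjects, each one whose only pain-free record follows rescue moves the percentage by 1/20 = 5 points. Once the condition is applied, the lower bound in step 2 fails too. The objective's percentage can fall below the highest timepoint percentage, because some of those responders no longer count.

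**The case against.** **The study is descriptive.** Protocol 14.1 specifies no formal hypotheses, so a missing deciding comparison is partly the design. This stands, and it limits the harm to ambiguous, selectable reporting. A descriptive objective still needs its named quantity reported.

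**A reader might infer that the plan never produces the any-timepoint result.** That goes too far. SAP 11.8.3.2 and 10.16 plan first-pain-free counts with paired differences, protocol 14.5 plans the two-way table, and the Kaplan-Meier curve shows the result approximately at 8 h. What remains is narrower: these outputs are exploratory, run to 24 h, have no rescue rule in the derivation and are not linked to objective 2.

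**A reader might infer an inflated false-positive rate from six timepoints.** The documents do not support it. SAP 11.8.2.5 and 10.16 name no test or interval for this endpoint. The textbook figure, 1 − 0.95^6 = 26.5%, is for six independent tests. Simulated exact McNemar tests in 20 pairs, under the rates assumed in step 3, gave about 4% to 7% for at least one of six and about 2% for the single any-timepoint test. None of these is an error rate of this plan.

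***Any* may have meant *each*.** This is possible, and the documents do not settle it. However, SAP 10.15.4 and 11.8.2.5 write *each* where they mean it, and the rescue condition would be missing on either reading.

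**Table 14.2.4 may already hold such a row.** Its shell is in the Data Display Plan, which is not among the documents. The criticism is of the SAP text only.

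**Conclusion.** The point holds as a mismatch between an objective and its analysis. The percentage named in secondary objective 2 is not pre-specified in endpoint 3, the responder flag or SAP 11.8.2.5. The no-rescue condition is missing from all three, so 4 h and 8 h successes may include relief after rescue. The nearest substitute is an exploratory table that must be summed by hand and lacks a rescue rule in its derivation.

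The mismatch itself rests on the text and needs no assumption. Its numerical size cannot be taken from the documents: the 40% to 75% range and the reversal use assumed counts, and the model ranges use assumed rates. How much rescue matters depends on its use in each treatment, which the plan does not predict. The primary endpoint is not affected by this point. The change is worth making because it is cheap and settles, before unblinding, what will be reported as the answer to objective 2.

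**What to change.** - **Flag.** In SAP 7.2, 10.15.4 and 11.8.2.5, add one flag per subject-period: NRS 0 or 1 at one or more of 0.5, 1, 1.5, 2, 4 or 8 h, with any timepoint after rescue intake counted as not pain-free. If the sponsor reads the objective as no rescue at all to 8 h, the SAP should say so before unblinding.
- **Reporting.** Present the flag as one row of Table 14.2.4 with the paired two-way table and difference of SAP 10.16, and name it as the summary for secondary objective 2.
- **Timepoint percentages.** Label them supportive and apply the same rescue rule at 4 h and 8 h.
- **If *each* was intended.** Reword the objective and still apply the rescue condition.

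**Cost.** One derived flag and one table row, from pain scores and rescue records the diaries already collect. The flag needs rescue ordered in time against the pain records. The documents do not say plainly that the clock time of rescue is recorded, so the SAP should also state what happens when the order is unknown. The downside is that some 4 h and 8 h responder percentages may be lower, and a favourable result at one timepoint becomes supportive only.
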